#### 8.7. Physical Examination

Not applicable

#### 9. PHARMACOKINETICS

Summary statistics for blood will be presented for maximum concentration (Cmax), area under the (activity-time) curve (AUC), clearance (CL), volume of distribution at steady-state (Vss), time to maximum concentration (Tmax), half-life(T1/2) [noncompartmental analysis], T1/2-alpha and T1/2-beta [2-compartment modelling], and mean residence time (MRT). Clearance and Vss will be body-weight normalized.

Percent of dose recovered in urine will be presented by collection intervals for the PK urine set. The following urinary kinetics will also be presented for this set: Tmax, Rate max, Rate last,  $T_{1/2}$  elim, and cumulative urine recovery by 4 and 8 hours post administration as % injected dose. The ratio of plasma-to-blood concentrations will be calculated per each subject/time-point.

#### 9.1. Derived Data

- Concentration of Reference Standard, µCi/mL =
  - (Decay Corrected pre injection reference standard of syringe prior to injection into flask—Decay Corrected post injection reference standard of syringe after injection into flask)/1000mL.
- Reference Standard CPM = F-DCFPyL reference standard (CPM) from PK\*Decay Correction factor for measurement time defined for 0-4 hours
- Average CPM for Reference standard= Average of 3 CPM results collected for F-DCFPyL std for 0-4 hours.
- Average CPM/ml for reference standard= Average CPM for reference standard/0.3
- Concentration of Reference Standard in CPM/ $\mu$ Ci = Average CPM/ml for reference standard/concentration of reference standard ( $\mu$ Ci/mL)
- For each blood, plasma and urine sample time, calculate:
  - $^{18}$ F-DCFPyL CPMb =  $^{18}$ F-DCFPyL CPM result at sample time\*correction factor for measurement time defined for the PK period the sample is drawn in
  - $CPM_b(ml) = CPM_b/0.3$

- CPM concentration( $\mu$ Ci/ml) = CPMb (ml) / Concentration of Sample in CPM ( $\mu$ Ci)
- Average CPM  $\mu$ Ci/ml = average CPM  $\mu$ Ci/ml within each unique nominal time
- Ratio of plasma to blood = Average CPM ( $\mu$ Ci/ml) for plasma/ Average CPM ( $\mu$ Ci/ml) for blood per unique sample nominal time
- For each urine sample, calculate:
  - Radioactivity excreted per collection interval ( $\mu$ Ci) = CPM ( $\mu$ Ci/ml) from urine\*urine collection volume (ml)
  - % Dose excreted = (Sum of Radioactivity exerted per collection interval( $\mu$ Ci) /(administered dose(mCi)\*1000))\*100
  - Average % dose excreted = average of individual % dose excreted per unique urine collection interval
  - Cumulative Average % dose excreted = sum of average % dose excreted over all unique urine collection intervals:
    - 0-4 hours = sum of average % dose excreted over 0-2 and 2-4 hours urine collection intervals
    - 0-8 hours = sum of average % dose excreted over all unique 0-2 and 2-4 hours urine collection intervals (0-2, 2-4, and 4-8 hours)

\_

Pharmacokinetic analyses will be conducted on pooled cohorts using the PK blood set and PK urine set.

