10.6. Pharmacokinetics

A total of 10 subjects from either cohort at the JHU site will complete the pharmacokinetics (PK) portion of the study. For detailed instructions on sample collection, processing, and analysis, please refer to the PK Manual.

A 4.5 mL blood sample will be collected at the following nine time points: pre-dose, 5 ± 2 m, 15 ± 2 m, 30 ± 5 m, 1 ± 0.25 hr, 2 ± 0.25 hr, 4 ± 0.25 hr, 6 ± 0.25 hr, and 8 ± 0.25 hr post-dose.

Urine samples will be collected over the following intervals: 0-2 hr, 2-4 hr and 4-8 hr post dose.

Whole body PET/CT scans will be collected at three time points: up to 17 minutes after PyL injection and prior to voiding, 1 ± 0.25 hr and 4 ± 0.25 hr post dose.

Procedure	Pre- dose	0 hr	5±2 m	15± 2 m	30± 5 m	1± 0.25 hr	2± 0.25 hr	3± 0.25 hr	4± 0.25 hr	6± 0.25 hr	8± 0.25 hr
¹⁸ F-DCFPyL Administration		Х									
Blood & Plasma Collection	X		Х	Х	Х	X	X		Х	Х	Х
Urine Collection		<	<x> <x></x></x>				>				
¹⁸ F-DCFPyL PET/CT Imaging			X			X			Х		

 Table 5:
 PK Sampling & Imaging Timepoints

Analysis will be generated as described below and in Section 12.5.4. Aliquots of blood, plasma and urine samples will be batch counted in an automated gamma counter immediately following the sample collection period. Resulting raw radioactivity counts will be converted into radioactivity concentrations using an aliquot of the dosing formulation as a reference standard.

Blood concentration-time data will be computed by non-compartmental analysis and pharmacokinetic parameters, e.g., C_{max} , AUC, CL, V_{ss} , and MRT will be generated. Ratios of blood to plasma radioactivity at each time point will be calculated.

The total amount of excreted radioactivity per urine collection interval will be calculated as a product of urine radioactivity concentration and volume, and then expressed as a percent of administered dose.

Metabolic profiles in urine will be determined using radio-chromatographic methods. The areas under the radio-chromatographic peaks corresponding to the parent compounds and putative metabolites, if applicable, will be used in the qualitative assessment of metabolic profiles in urine.

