#### 5.5.10. Decay Corrected Dose at Time of Administration

The calculations in this section will need to be performed for the pre- and post- injection values for F-DCFPyL administration as well as pre- and post- injection from the Syringe to the flask for reference values.

If a decay correction was performed for the pre-or post- dose values then Correction Factor =1. Otherwise:

```
 \text{Correction Factor} = e^{(\ln(2)*(pre\ or\ post\ injection\ time(min)-injection\ time\ (min)))}/_{110\ min}
```

where the above formula will be calculated for each of the following pre and post injection times:

pre-dose

post dose

syringe prior to flask syringe post flask

start of measurement times with each PK period

Convert all pre- and post- injection amounts to mCi: 37MBq = 1mCi

If there was no post decay correction then:

```
Decay Corrected Dose at time of Administration = (pre injection amount (mCi)*Correction Factor Pre Dose)- \frac{Post\ injection\ amount\ (mCi)}{Correction\ Factor\ Post\ Dose}
```

If there was a post decay correction then:

Decay Corrected Dose at time of Administration(mCi) = (pre injection amount(mCi) – post injection amount(mCi))

Calculate decay corrected doses at time of administration in both mCi for all subjects and MBq for all subjects.

The Decay corrected pre-injection Reference Standard of syringe prior to injection into flask = amount (μCi) in syringe prior to injection into flask\*Correction Factor of syringe prior to flask.

The Decay corrected post-injection Reference Standard of syringe after injection into flask = amount ( $\mu$ Ci) in syringe after injection into flask\*Correction Factor of syringe after flask.

The decay corrected reference standards are only needed in µCi.

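### SAP 9.1 gives no correct written route from gamma-counter counts to concentration: the decay-corrected reference count is never carried forward, and samples are divided by an undefined term

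*SAP*

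**What the plan says.** Protocol 10.6 has blood, plasma and urine aliquots batch counted after the collection period, with raw counts "converted into radioactivity concentrations using an aliquot of the dosing formulation as a reference standard". It gives no formula and refers to a PK Manual for detail.

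SAP 5.5.10 supplies the decay factor, with a 110-minute half-life, and lists the times at which it is calculated, including "start of measurement times with each PK period". The activity of the standard is put on the injection-time scale there: "The Decay corrected pre-injection Reference Standard of syringe prior to injection into flask" is the measured amount times its factor, and the post-injection residue is treated the same way.

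SAP 9.1 then builds the conversion:

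- *Reference Standard CPM* is the standard's count times the "Decay Correction factor for measurement time defined for 0-4 hours".
- The average for the standard is the "Average of 3 CPM results collected for" the standard over 0–4 hours.
- "Average CPM/ml for reference standard= Average CPM for reference standard/0.3".
- That value divided by the standard's activity in µCi/mL gives a calibrator in CPM per µCi.
- Each sample count is multiplied by the "correction factor for measurement time defined for the PK period the sample is drawn in", giving CPMb, and divided by 0.3.
- The sample concentration in µCi/mL is that result divided by "Concentration of Sample in CPM" (µCi).

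**The concern.** Two links in this chain are broken as written. The corrected reference count is defined but does not appear by name in any later formula. The calibrator in CPM per µCi is also derived and then not used; its place is taken by a term with no definition.

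The first break matters because the other two ingredients, the standard's activity and the sample counts, are both referred back to injection. A calibrator built from uncorrected standard counts would mix two time points and be too small.

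The blood parameters are secondary endpoint 6, and urinary excretion falls under secondary objective 5. SAP 7.7.4 leaves the PK parameters to an external analyst, so the written derivation has to stand alone. The error would also be hard to see in the blood data: only a 0–4 h standard is used, so one multiplier applies to all of a subject's samples, and the shape of the curve and the half-lives would look normal.

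**Working it through.** The documents state no concentration or error size, so there is no figure to reproduce. The check follows the formulas through.

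**Inputs**

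- Decay factor CF(t) = exp(ln 2 × t/110) = 2^(t/110), t in minutes from injection (SAP 5.5.10). The layout of the formula is broken in the text; the division by 110 is read as inside the exponent.
- Aliquot divisor 0.3 for standard and samples (SAP 9.1).
- Time of counting the standard: not given. Protocol 10.6 places counting after the collection period, and SAP 9.1 ties the standard to 0–4 h. A time near 240 min is therefore an assumption. The lower edge of the 4 ± 0.25 h sampling window is 225 min.

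**Units.** (CPM/mL) ÷ (CPM/µCi) = µCi/mL. Of the quantities defined in SAP 9.1, only the reference calibrator gives the stated unit.

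**Algebra.** Let E be the counter's CPM per µCi, S the standard's activity concentration at injection, and C the true sample concentration at injection.

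- Raw standard count: E × S × 0.3 / CF(t).
- Calibrator from raw counts: (E × S / CF(t)) / S = E / CF(t).
- Calibrator from corrected counts: (E × S) / S = E.
- Corrected sample count per mL: E × C.
- Concentration with the raw calibrator: E × C ÷ (E / CF(t)) = C × CF(t).
- Concentration with the corrected calibrator: E × C ÷ E = C.

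**Numerical check** with arbitrary values E = 1,000,000, S = 0.1, C = 0.5 and t = 240: the corrected calibrator returns 0.50 and the raw calibrator 2.27, a ratio of 4.54. E and S cancel, so their values do not matter.

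| Standard counted at (min) | Multiplier if raw counts are averaged | Multiplier if corrected counts are averaged |
|---|---|---|
| 0 | 1.00 | 1.00 |
| 60 | 1.46 | 1.00 |
| 120 | 2.13 | 1.00 |
| 225 | 4.13 | 1.00 |
| 240 | 4.54 | 1.00 |
| 270 | 5.48 | 1.00 |
| 300 | 6.62 | 1.00 |

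The multiplier reaches 2 at 110 min and 3 at 174 min.

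**Effect on the parameters.** The administered dose is derived separately from syringe measurements and does not carry the factor.

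- Cmax, AUC and percent of dose excreted are multiplied by CF(t).
- CL = dose/AUC and Vss = CL × MRT are divided by CF(t).
- Tmax, half-lives and MRT do not depend on a constant multiplier.
- The plasma-to-blood ratio does not change, because the factor cancels.

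**The case against.** The best defence is sequence. The averaging line comes directly after the line that corrects the standard's counts for the same 0–4 h period, and the correction has no other purpose. On that reading the three results are the corrected ones, and the error from this step is nil. The wording does not exclude this. Against it, the sample line uses CPM result for a count not yet corrected, and gives the corrected value its own symbol, which is carried forward. Raw counts are therefore the literal reading, but not the only one. SAP 5.5.10 has no rule for counter output that is already corrected, and protocol 10.6 calls the counts raw.

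A reader might infer that samples are divided by their own value. The text does not say so. Self-division would give a constant of 1, which is unusable rather than several-fold wrong. The section writes CPMb(ml) for a per-mL quantity, so CPM (µCi) most naturally means CPM per µCi, the unit of the unused calibrator. The probable fault is one wrong word in the label.

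A reader might also infer that all concentrations will be several-fold wrong. That needs both the raw-count reading and a late counting time, and the documents settle neither.

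The reach is limited too: 10 subjects at one site, descriptive summaries, and a PK Manual outside these documents that may state the chain correctly. A large inflation could show up in urine: at 4.54-fold, any true recovery above 1/4.54 = 22% would be reported as more than 100%. These points limit the consequence; they do not repair the two formulas.

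**Conclusion.** The point holds as a defect in the written derivation with a conditional size. The unused corrected reference count and the undefined divisor are plain on the page, and the second needs correcting however the first is read.

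If raw standard counts are averaged and the reference calibrator is the divisor, blood Cmax and AUC and urinary percent dose are overstated, and CL and Vss understated, by 2^(t/110). That is about 4.1 to 4.5 if the standard is counted at 225 to 240 min, 2.1 at 120 min and 6.6 at 300 min, all on an assumed t. If the corrected counts are averaged, the factor is 1.

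SAP 3.2.2 limits secondary endpoint 6 to parameters from blood, so urinary recovery is affected only as part of secondary objective 5. The primary endpoints are untouched.

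**What to change.** Reword two lines of SAP 9.1:

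- Average CPM for reference standard = average of the 3 decay-corrected *Reference Standard CPM* values.
- CPM concentration (µCi/mL) = CPMb(ml) / *Concentration of Reference Standard in CPM/µCi*.

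Confirm that the PK Manual and the external analyst's calculation follow the same route. The cost is two lines of SAP wording and that check; no new data are needed.

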# 10. PLANNED TREATMENT SAP CHANGES THAT DIFFER FROM THE PROTOCOL

- Screened population renamed to consented population as the definition states all subjects need to provide consent and not screening data.
- The Evaluable set was updated to state that subjects in Cohort A are required to have a prostatectomy and lymphadenectomy.
- The Change in Planned Protocol Procedure Set was added as a subject population to capture the subjects who had a change in the planned protocol procedure.
- The PK Evaluable set was divided into two groups: The PK Blood Set and the PK Urine set, as a subject could meet the criteria for one of these, but not the other.
- 'PPV of 18F-DCFPyL PET/CT imaging in subjects with corresponding histopathology that is outside the planned protocol surgical template or biopsy site' was updated to 'PPV of 18F-DCFPyL PET/CT imaging in subjects with corresponding histopathology for subjects who had a change in planned treatment per Cohort assignment'. Subjects may undergo a planned protocol procedure defined per the other cohort.
- The number of lesions per subject plotted against PSA and baseline testosterone for each of the 3 central imaging core lab readers will no longer be performed.
- SUVmax, SUVpeak, SUVr will no longer be summarized by subgroups: Previous radiation therapy (yes/no), Previous hormonal therapy (yes/no), or Previous chemotherapy (yes/no). Most subjects will be from cohort B only.
- Sensitivity will no longer be summarized by previous radiation therapy, previous hormonal therapy or previous chemotherapy. Since it is no longer the primary endpoint and it's not appropriate to combine cohorts for this analysis, it is no longer of interest.
- The following was added for PK: Additional blood concentration time data will be fitted into a two-compartmental model to calculate T1/2-alpha and T1/2-beta. For % of injected dose recovered per each urine collection interval per subject will be used to calculate Tmax, Rate max, Rate last, T1/2elim, and cumulative urine recovery if feasible.

## 12. APPENDIX

## 12.1. Table of Contents for Data Display Specifications

Table 4 contains a list of tables, listings and figures proposed for this study.

**Table 4: List of Tables, Listings and Figures** 

Number	Title	
14.1-1	Subject Enrollment and Disposition, Consented Subjects	
14.1.1: Baseline Summaries – Safety Set		
14.1.1-1	Demographics and Baseline Characteristics, Safety Set	
14.1.1-2	Prostate Cancer History, Safety Set	
14.1.1-3	Medical History, Safety Set	
14.1.1-4	Prior Prostate Cancer Therapies, Safety Set	
14.1.1-5	Prior Surgery, Safety Set	
14.1.1-6	Conventional Imaging at Baseline, Safety Set	
14.1.1-7	Baseline Medication Use, Safety Set	
14.1.2: Ba	seline Summaries – Evaluable Set	
14.1.2-1	Demographics and Baseline Characteristics, Evaluable Set	
14.1.2-2	Prostate Cancer History, Evaluable Set	
14.1.2-3	Medical History, Evaluable Set	
14.1.2-4	Prior Prostate Cancer Therapies, Evaluable Set	
14.1.2-5	Prior Surgery, Evaluable Set	
14.1.2-6	Conventional Imaging at Baseline, Evaluable Set	
14.1.2-7	Baseline Medication Use, Evaluable Set	
14.1.3: Ba	seline Summaries – Per Protocol Set	
14.1.3-1	Demographics and Baseline Characteristics, Per Protocol Set	
14.1.3-2	Prostate Cancer History, Per Protocol Set	
14.1.3-3	Medical History, Per Protocol Set	
14.1.3-4	Prior Prostate Cancer Therapies, Per Protocol Set	
14.1.3-5	Prior Surgery, Per Protocol Set	
14.1.3-6	Conventional Imaging at Baseline, Per Protocol Set	
14.1.3-7	Baseline Medication Use, Per Protocol Set	
14.2.1: Pr	imary Efficacy – Evaluable Set	
14.2.1-1	Sensitivity and Specificity of the Pelvic Lymph Nodes for the Subjects in Cohort A, Evaluable Set	

14.2.2: Secondary Efficacy- Evaluable Set or PK Serum Set			
14.2.2-1	Diagnostic Testing for Secondary Endpoints, Evaluable Set		
14.2.2-2	Summary of Imaging Detection Rates for Lesion Counts by Region- Evaluable Set		
14.2.2-3	Summary of Pharmacokinetic Parameters for Cycle 1, Day1- PK Blood Set		
14.2.3: Ex	ploratory Efficacy		
14.2.3-1	SUV Responses at Baseline- Evaluable Set		
14.2.3-2	SUVR Responses at Baseline – Evaluable Set		
14.2.3-3	SUV Responses by Histology Outcomes- Evaluable Set		
14.2.3-4	SUV Responses and Volume at Baseline by PSA Groups- Evaluable Set		
14.2.3-5	SUV Responses and Volume at Baseline by Gleason Score Groups at Time of Prostatectomy- Evaluable Set		
14.2.3-6	SUV Responses and Volume at Baseline by Testosterone Groups-Evaluable Group		
14.2.3-7	Specificity and Sensitivity of the Prostate Gland for Cohort A- Evaluable Set		
14.2.3-8	Shift in Change of Management Questionnaire- Safety Set		
14.2.3-9	Analysis of Change in Management Questionnaire- Safety Set		
14.2.3-10	PPV and Positive Imaging from any tissue compared to histology for both Cohorts Combined -Change in Management Set		
14.2.3-11	Summary of Imaging Results-Safety Set		
14.2.3-12	Summary of Histology Results- Safety Set		
14.2.3-13	Summary of Procedures- Safety Set		
14.2.3-14	Inter-Reader and Intra-Reader Variability for Cohort A- Evaluable Set		
14.2.4: Ef	14.2.4: Efficacy- Per Protocol Set		
14.2.4-1	Specificity and Sensitivity of the Pelvic Lymph Nodes for the Subjects in Cohort A- Per-Protocol Set		
14.3.1: Ad	lverse Events- Safety Set		
14.3.1-1	Summary of Treatment Emergent Adverse Events, Overall and by Cohort -Safety Set		
14.3.1-2	Most Frequent (>5% Overall) Treatment Emergent Adverse Events, Overall and by Cohort-Safety Set		
14.3.1-3	Treatment Emergent Adverse Events Overall and by Cohort- Safety Set		
14.3.1-4	Serious Treatment Emergent Adverse Events Overall and by Cohort- Safety Set		
14.3.1-5	Drug Related Treatment Emergent Adverse Events Overall and by Cohort- Safety Set		
14.3.1-6	Treatment Emergent Adverse Events where Severity Grade>=3, Overall and by Cohort-Safety Set		
14.3.1-7	Treatment Emergent Adverse Events by Severity Grade, Overall – Safety Set		

14.3.2: Lis	sting of Deaths and Other Serious and Significant Adverse Events- Safety Set
14.3.1-1	Listing of Treatment Emergent Adverse Event Leading to Discontinuation or Death- Safety Set
14.3.1-2	Listing of Treatment Emergent Adverse Events Deemed Serious or With a Grade 3 or Above- Safety Set
14.3.4: Ab	onormal Laboratory Value Listing
14.3.4-1	Listing of Abnormal Hematology Results – Safety Set
14.3.4-2	Listing of Abnormal Chemistry Results- Safety Set
14.3.5: Vi	tal Signs
14.3.5-1	Summary and Change from Baseline in Vital Signs- Safety Set
14.3.6: Ot	her Safety Data
14.3.6-1	Summary and Change from Baseline in Hematology Results- Safety Set
14.3.6-2	Summary and Change from Baseline in Chemistry Results- Safety Set
14.3.6-3	Clinical Laboratory Shift Table: Chemistry- Safety Set
14.3.6-4	Clinical Laboratory Shift Table: Hematology- Safety Set
14.3.6-5	Summary and Change from Baseline in ECG Parameters- Safety Set
14.3.6-6	Concomitant Medications- Safety Set
14.3.6-7	Study Drug Exposure- Safety Set
14.4: PK I	Evaluations
14.4-1	Percent of Dose Recovered in Urine per Collection Interval -PK Urine Set
14.4-2	Summary of Urinary Kinetics- PK Urine Set
Listings	
16.2.1-1	Listing of Discontinuations – Consented Population
16.2.2-1	Listing of Protocol Deviations – Safety Set
16.2.3-1	Listing of Subjects Excluded from the Evaluable Set Used for Efficacy- Safety Set
16.2.4-1	Listing of Demographics- Consented Set
16.2.5-1	Listing of Blood PK by Nominal Blood Draw Times – PK Blood Set
16.2.5-2	Listing of Plasma PK by Nominal Blood Draw Times- PK Blood Set
16.2.5-3	Listing of Blood PK Parameters- PK Blood Set
16.2.5-4	Listing of Urinary Kinetics- PK Urine Set
16.2.5-5	Listing of Urine PK by Collection Intervals- PK Urine Set
16.2.5-6	Listing of Decay Corrected Dose – Safety Set
16.2.5-7	Listing of Compliance- Safety Set
16.2.6-1	Listing of Diagnostic Performance – Evaluable Set

## Progenics Pharmaceuticals, Inc. Statistical Analysis Plan – Protocol PyL-2301

September 5, 2018

16.2.7-1	Listing of Adverse Events- Safety Population	
16.2.8-1	Listing of Laboratory Parameters- Safety Set	
Figures		
riguies
